#### If the patient is untraceable at the time of the scheduled follow-up visit

Re-schedule the visit, where possible either by phone call or home visit. If patient wishes to withdraw from treatment, complete treatment withdrawal form.

#### For participants in high-risk risk stratum group in Weeks 2, 4, 8, 12, 16 only

- Collect one biochemistry blood tube for liver function test.
- Record collection date and time in eCRF
- Despatch to laboratory
- Record results in eCRF. The sample should arrive to lab within 24 hours at a suitable temperature.

#### Unexpected events during treatment

- Management of adverse events is described below.
- Lost or misplaced doses of the medication should be replaced after checking that they cannot be found and checking with the study Doctor.
- If the participant states that he/she vomited after taking the study drug, this should be discussed with the study doctor. This may be an adverse event.

### **Indications for cessation of TB preventive treatment**

If a participant experiences one or more of the conditions/situations listed below, the Investigator will permanently discontinue study drugs

- 1) Participants deprived of freedom by an administrative or court order
- 2) SAE-related to the study drug.
- 3) Diagnosed with (and treated for) active TB
- 4) Pregnancy reported by the participant

TEST AND TREAT TO END TB Protocol, V2.0 14th September 2021 5) Onset of a condition that would have made the participant ineligible for commencing TB preventive treatment.

# Survey to measure prevalence of pulmonary TB (primary endpoint)

Two years after the intervention (2023), we will undertake a prevalence survey in both active intervention and control groups. This survey will be analogous to the survey conducted in the final year of the ACT3 study (25).

The survey will begin with household enumeration census (as described above, page 14). The screening team will conduct a series of meetings with local health and government officials to brief them on the procedures and to generate political and community support. The residents of the Ap will be informed about the survey by announcements broadcast over loudspeakers and banners deployed throughout the subcommune.

A census of all households in all participating sub-communes (Aps), in both intervention and control arms, will be conducted. The nature of the census will be explained and verbal consent to proceed will be sought and documented in the eCRF. With consent, we will collect information on names, year of birth or age, sex and phone number of each household member. At this time household members will be provided with written information about the survey. No identifying information will be collected from participants who are incapable of providing and from those who decline.

All consenting, eligible individuals aged  $\geq 15$  yrs, will be asked about the following symptoms (on the day of testing and on any day in the previous two weeks):

- Cough
- Sputum production
- Coughing up blood.

Each individual who has given consent will be asked to produce a single, spontaneously expectorated sputum specimen.

All specimens will be transported to the central laboratory, stored in at 4oC and tested within 48 hours using the Xpert Ultra system (Cepheid).

Those who test positive on Xpert Ultra will be invited to attend the provincial TB centre for further clinical evaluation. They will also be requested to produce two further sputums for mycobacterial culture and to have a chest radiograph performed.

Endpoints will be defined based on these results, as descripted above (see page 11). Those who are unable to produce sputum for Xpert Ultra testing will be assumed not to have pulmonary TB for the purposes of this endpoint evaluation.

## Survey to measure prevalence of latent TB in children

The purpose of this survey is to estimate the effect of the intervention on TB transmission, as indicated by the difference in prevalence of latent TB infection among children in the intervention and control arms four years after the commencement of the intervention in the intervention arm.

The study population will be children who were born between 2008 and 2016, who would be aged 5 to 13 in 2021 (when the trial begins). The proposal is to measure the prevalence of latent TB infection in this population in 2025 (four years after commencing the intervention), when the participants will be aged 9 to 17 years.

Eligible participants will be children who

- 1. were born between 1st January 2008 and 31st December 2016;
- 2. are resident in the active intervention or control clusters during the population enumeration in 2021-2022;
- 3. whose parents or legal guardians are capable of giving informed consent
- 4. who themselves are capable of giving assent.

The presence of latent TB infection will be assessed using the QuantiFERON®-TB Gold Plus test kit, which will be used in accordance with the manufacturer's instructions.

We will randomly select 16 eligible participants per sub-commune. After gaining written informed consent (from parent or guardian) and assent (from the child), 1 mL of blood will be collected into each of the four test tubes, which will be transferred to the laboratory.

Study Year	Semester	Activity*	Study Population
One	Oct21-Mar22	All persons aged 5 a	
	Apr22-Sep22	Test & Treat intervention	over in active intervention
Two	Oct22-Mar23		sub-communes
	Apr23-Sep23		
Three	Oct23-Mar24		Persons aged 15 and over
	Apr24-Sep24	I D prevalence survey	in the active intervention and control sub-
Four	Oct24-Mar25		communes
	Apr25-Sep25		
Five	Oct25-Mar26	LTBI prevalence survey	Children born 2008- 2016 ** in active intervention and control sub-communes

## Timeline

\* "Test & Treat" is the screening intervention; "TB prevalence survey" is to measure the prevalence of active TB disease; "LTBI prevalence survey" is to measure the prevalence of latent TB infection.

\*\* Aged 5-13 years at start of trial, now aged 9-17 years

# 9) Study treatment

Those eligible and consenting for treatment of LTBI in the active intervention arm will receive the 3HP regimen. This regimen includes oral treatment with

- Once weekly oral combination rifapentine / isoniazid
- This table of weight range dosage applies to children aged 5 years to < 15 years of age

TEST AND TREAT TO END TB Protocol, V2.0 14th September 2021

Weight range	Weekly rifapentine dose	Weekly isoniazid dose	Number of combination tablets
			(300mg/300mg)
10–14 kg	300 mg	300 mg	1
14.1–25 kg	450 mg	450 mg	1.5
25.1–32 kg	600 mg	600 mg	2
32.1–49.9 kg	750 mg	750 mg	2.5
≥50 kg	900 mg	900 mg	3

• All participants aged 15 years of age and older receive a once weekly dose of 900mg rifapentine and 900mg isoniazid.

Treatment will be dispensed once weekly for 12 weeks by a study team member based in the Ap.

This treatment regimen has been shown to be safe and effective in a phase 3 clinical trial (30) and is approved for treatment of LTBI in children and adults by the US Food and Drug Administration (FDA). It is recommended in US Centre for Disease Control (CDC) (33) and World Health Organization (WHO) (34) guidelines and is approved for use in Vietnam for treatment of LTBI in contacts of patients with active TB, and other high risk populations.

#### Treatment administration

The procedure for treatment administration is described on page 20.

#### Monitoring adherence to therapy

The importance of adherence will be emphasized during each week visit. If participants are non-adherent, the study staff should endeavour to identify any problems contributing to non-adherence (e.g. side effects) and seek support from the clinical staff to manage the issue. Adherence will also be assessed by direct phone call or face to face interview.

If contacts do not attend a scheduled appointment during the period of their treatment or respond to a phone call and arrange an alternative time, then a household visit will be arranged within the next 7 days. If contacts miss one appointment (by 7 days or more after the due date) the Trial Coordinator will be notified and a plan made to ensure follow-up is completed. The outcome of visit attempts will be documented and included in a report to the Trial Steering Committee. An attempt will then be made to continue follow-up at the next scheduled weekly follow-up time.

#### Follow-up the post-treatment period

The end of treatment date will be either

- The date on which the 12th dose of treatment is taken or
- 16 weeks after treatment initiation

whichever comes first.

The final visit should be scheduled two weeks after the "end of treatment" date.

At this visit

• Interview the participant using the "Symptom Screening prior to Administering Medications" questionnaire. If the participant responds positively to any of the

TEST AND TREAT TO END TB Protocol, V2.0 14th September 2021 symptoms on the checklist, follow instructions in **Adverse event management** and submit the **eCRF "Adverse events**" form within 24 hours (even if unsure about whether it is an adverse event). If the Treatment Officer is unsure about whether a participant has had an Adverse Event, or whether Active TB should be investigated, discuss with the Medical Advisor by telephone.

• Complete the "Close-out" form, recording the total medication the participant had during the treatment, any adverse event occurred and the outcomes of adverse event.

### Packing and labelling

Packaging and labelling of the medicinal products will be performed by the Woolcock Institute in Vietnam in accordance national regulatory requirements. Isoniazid and rifapentine are commercially available.

#### Dispensing and product accountability

The trial medication delegate will maintain dispensing logs detailing the dates, quantities and batch numbers of dispensed and returned study drugs for each participant. The trial medication delegate will also manage the overall drug accountability.

#### Missed doses

If a missed dose occurs  $\leq 3$  days past the scheduled dosing time, then the participant will be administered the missed dose and the next dose should be taken as scheduled. If the missed dose is discovered > 3 days past the scheduled dosing time, re-dose and re-schedule next dose to 1 week after the current dose.

# 10) Laboratory assessments

All below listed blood tests will be performed by the central and local laboratory

Test	Reference value
Full blood count	
WBC	3.70-10.1 (10  /µL)
NEU	39.3 - 73.7%
LYM	18.0 - 48.3%
MONO	4.40 - 12.7%
EOS	0.6 - 7.30%
BASO	0.0 - 1.70%
RBC	4.06-4.69 (10  /μL)
RET	0.3 - 2.0%
HGB	12.9- 14.2 g/dL
НСТ	37.7 - 53.7%
MCV	81.1 - 96.0 fL
МСН	27.0 - 31.2 pg
МСНС	31.8 - 35.4 g/L
RDW	11.5 - 14.5%
PLT	155-366 (10  /µL)
Liver Function Tests	
Albumin	38 – 54 g/l
GOT (AST)	10 - 37 U/L
GPT (ALT)	10 - 40 U/L
Gamma GT	12 - 45 U/L
Bilirubin (total)	< 1 mg/dl

# 11) Adverse event reporting

# **Definition of terms**

## Adverse Event (AE)

Any untoward medical occurrence in a patient or clinical investigation subject administered a pharmaceutical product. It does not necessarily have a causal

TEST AND TREAT TO END TB Protocol, V2.0 14th September 2021 relationship with this treatment. An adverse event can be any unfavourable and unintended sign, symptom, or disease temporally associated with the use of a medicinal (investigational) product, whether or not related to the medicinal (investigational) product.

An adverse event is any adverse occurrence that occurs after study participant signs the consent form, even if it may not be directly related to the treatment.

#### Adverse Event of Special Interest (AESI)

An adverse event (serious or non-serious) of scientific and medical concern specific to the Sponsor's product or program, for which ongoing monitoring and rapid communication by the Investigator to the Sponsor may be appropriate. Such events may require further investigation in order to characterise and understand them. AESIs may be added or removed during a Study by protocol amendment.

#### **Adverse Drug Reaction (ADR)**

Adverse event that is assessed as possibly, probably or certainly attributable to the study medication.

Adverse events that occur more than 14 days after the date of taking the last dose of the study drug will be deemed to be unrelated to the study drug.

#### Serious adverse event (SAE)

Any adverse event that

- a) results in death,
- b) is life-threatening,
- c) requires inpatient hospitalization or prolongation of existing hospitalization,
- d) results in persistent or significant disability/incapacity,
- e) is a congenital anomaly/birth defect,
- f) where the investigator or trial medical officer considers that medical intervention is required to prevent one of the preceding circumstances from arising,
- g) where the investigator or trial medical officer considers the circumstances are serious for other medical reasons.

#### **Unexpected Adverse Event (UAE) / Unexpected Adverse Drug Reaction (UADR)**

An adverse event or adverse reaction, the nature or severity of which is not consistent with the applicable product information (Product Information/Data Sheet). An expected ADR with a fatal outcome should be considered unexpected unless the local/regional product labelling specifically states that the ADR might be associated with a fatal outcome.

#### Serious Unexpected Suspected Adverse Drug Reactions (SUSARs)

An adverse event that meets the criteria for a serious adverse event (SAE) and also for unexpected adverse drug reaction; that is:

#### A. It is serious

- a. Results in death,
- b. Is life threatening,
- c. Requires inpatient hospitalisation or results in prolongation of existing hospitalisation;
- d. Results in persistent or significant disability/incapacity,
- e. Is a congenital anomaly/birth defect, or
- f. Is a medically important event or reaction.

TEST AND TREAT TO END TB Protocol, V2.0 14th September 2021 AND

B. It is attributable to the study medications / intervention (possibly, probably or certainly)

AND

C. It is unexpected, that is, it is not consistent with the applicable product information (the Investigator's Brochure for an unapproved investigational medicinal product or Product Information/Data Sheet for an approved product)

## Framework

The following committees, that are relevant to the patient safety and pharmacovigilance will oversee the trial:

- a) a trial management committee (TMC), comprising the senior investigators and trial management staff, who will conduct the day-to-day operations of the trial;
- b) a trial steering committee (TSC), including independent expert members and chair, who will review and approve protocols and key study documents as well as reports from the IDMC;
- c) an independent data monitoring committee (IDMC), who will review safety and efficacy data, independent of the TMC, and provide advice to the TMC and the TSC; and
- d) an expert clinical panel (ECP), who will review individual adverse event data, adjudicate event severity and attribution to study drug and report to the IDMC.

## Adverse events of special interest in this study

- The AESI for rifapentine are:
  - hepatotoxicity and
  - systemic drug reaction/hypersensitivity reaction.

Systemic reactions have been reported in 3.5% of patients taking rifapentine(35). In a recent study, symptoms occurred after a median of 3 doses, 4 hours after the dose; median time to resolution was 24 hours.

The definition of a systemic drug reaction will that used in the PREVENT study (35):

- hypotension (systolic blood pressure <90 mm Hg), urticaria (hives), angioedema, acute bronchospasm, or conjunctivitis (red eyes); OR
- > four of the following symptoms occurring concurrently (more than one of which had to be grade 2 or higher): weakness, fatigue, nausea, vomiting, headache, fever, aches, sweats, dizziness, shortness of breath, flushing, or chills.

AEs that meet either of the above criteria were termed systemic drug reactions.

There are no adverse events of special interest for isoniazid.

## Expected adverse drug reactions

This will be based on registered product information for isoniazid and on the Investigators Brochure for rifapentine. Currently, these identify the following adverse effects as expected with the study drugs.

Rifapentine*	Isoniazid
Hypersensitivity reactions	Hepatitis
Hepatotoxicity	

astrointestinal ymptoms
eripheral neuropathy
nmunologic reactions
e

\* The following additional adverse events have also been observed when rifapentine has been taken in combination with other anti-TB drugs: neutropenia, lymphocytopenia and anaemia.

#### **Pregnancy during treatment**

All pregnancies should be reported if they occur between the time the participant signs the consent form and 2 weeks after last dose. The "Pregnancy form" in the RedCAP eCRF should be used to report as follows:

- Initial report: to be completed within 24 hours of study staff becoming aware of the pregnancy.
- Follow up report: to be completed within one month after the end date of pregnancy

Any complication during pregnancy period that meets the criteria for SAE will be reported as SAE, SAE form will be completed.

## Reports

#### Vietnamese IRB and Ministry of Health

In accordance with Circular 29/2018/TT-BYT dated 29 October 2018, issued by MOH, details of all SAEs will be reported to Principal Investigator in Viet Nam, the responsible Institutional Review Board (IRB) in Viet Nam, the Ministry of Health (MOH) and the National Centre of Drug Information and Adverse Drug Reactions Centre according the following timetable:

- For all SAEs that are life-threatening or result in death, initial report must be reported to the MOH within 7 working days of event notice;
- For other SAEs, initial report must be sent to MOH within 15 working days of event notice;
- All SAE need to be informed to National Lung hospital EC within 24 hours (according to Vietnam national guideline for pharmacovigilance, 2015).
- Progress of SAEs must be updated via follow up reports until study participants are recovered.
- All non-serious AEs occurring in Viet Nam must be recorded, summarized and reported in a periodic report or study outcome report to be sent to the MOH's IRB and the Scientific and Education Department in the MOH.

#### **University of Sydney HREC**

The Trial Safety Officer is responsible for notifying the University of Sydney HREC of the following:

- All SAEs, within 72 hours of study staff becoming aware
- SUSARs, a line listing of all SUSARs at six monthly intervals
- Serious breaches should be reported to the reviewing HREC, usually by the Sponsor, within 7 calendar days of confirming a serious breach has occurred.

## **Reports to Data Safety Monitoring Committee**

The Trial Safety Officer, working with the DSMB statistician, is responsible for preparing, at six-monthly intervals, an aggregate report of all AEs including their SOC, grade, outcome and attribution to study drug.

The DSMB will review these, and other, data and make recommendations to the Trial Management Committee about the conduct of the trial. The report of the DSMB will be provided to the University of Sydney HREC.

# 12) Data analysis

Primary study objective is to estimate, among people living in Ca Mau Province, the effect of universal testing for and treatment of LTBI, together with active case finding **and treatment** for TB, on the population prevalence of **pulmonary** TB after **two** years.

The analysis will be by intention-to-treat. We will use a two-level (sub-commune and household) hierarchical generalised linear model with a Poisson error distribution to test the effect of treatment group allocation on number of prevalent cases of pulmonary TB in persons aged  $\geq 15$  years. Treatment group allocation will be the main (fixed) effect. Clusters will be treated as a random intercept term. The enumerated cluster population aged  $\geq 15$  years will be the offset. A p value < 0.05 will be treated as significant. No covariates will be included in the primary analysis. Prevalence rate ratios will be estimated with 95% confidence intervals, adjusted for clustering.

A secondary objective is to estimate the incidence of adverse events attributable to 3HP preventive therapy (safety analysis). The incidence of all adverse events grade 3 or higher, together with specific, expected adverse events in the intervention group will be enumerated and reported as rates per person-year of participation in the study.

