# Study setting and population

Vietnam has a nationally administered, centralised TB control program administered by the National TB Program. Most TB cases are diagnosed and managed at district level, where the diagnosis of pulmonary TB is based on sputum smear microscopy for people presenting with symptoms of TB. The standard treatment regimen for TB is oral isoniazid, rifampicin, pyrazinamide, and ethambutol for two months followed by isoniazid, rifampicin and ethambutol for four months.

The study will be conducted in Ca Mau, the southern-most province of Vietnam, which has a population of 1,216,400 people living in 101 communes within nine districts. In 2017, there were 1,045 reported cases of pulmonary TB in Ca Mau. Multi-drug resistant (MDR) TB (n=21, 2.0% in 2017) and HIV co-infection (n=19, 1.8% in 2017) are both relatively uncommon in Ca Mau. After our recent RCT in Vietnam (17\*), active case finding in household contacts is being scaled up and is being established in Ca Mau under the direction of AI [name] and CI [name].

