## Cluster allocation to treatment groups

The selected clusters will be randomly assigned to active intervention and control status, again stratified by district and by population size (32). This will ensure both representative selection and balanced allocation of clusters from within the province.

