# Sample size and study power

## Primary outcome

The intra-class (cluster) correlation coefficient for prevalent TB cases in the first year of screening of the ACT3 study was 0.0091. The prevalence of TB in the control clusters screened for the first time in 2017-18 was 0.233%. The average number of eligible participants in each cluster was 720. Active case finding alone was able to achieve a 50% reduction in prevalence over the four years study period. We expect that the composite intervention proposed here, which additionally includes treatment of the reservoir of latent TB infection, will achieve at least a 75% reduction.

We estimate that 104 clusters in each group, that is 74,800 eligible participants in each group, will be required in the final prevalence survey to have 90% power to detect a 75% lower prevalence of TB in the active intervention group, compared to the control group, as significant at the 5% level (two-sided test, PASS 2015 software, "Two proportions in a cluster-randomized design").

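### Clusters are randomised within district and population-size strata, but the primary model leaves the strata out, so its interval is too wide to the extent that strata predict TB prevalence

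*Protocol*

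**What the plan says.** Protocol section 7, Cluster allocation to treatment groups, says that the selected clusters are "randomly assigned to active intervention and control status, again stratified by district and by population size". The province has nine districts (section 6, Study setting and population). The number of size strata is not given.

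Section 12, Data analysis, specifies a hierarchical Poisson model. Its fixed part is the arm alone: "Treatment group allocation will be the main (fixed) effect". Its random part is the cluster: "Clusters will be treated as a random intercept term". The enumerated population aged 15 and over is the offset. It adds: "No covariates will be included in the primary analysis".

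The sample size (section 12, Primary outcome) takes an ICC of 0.0091, control prevalence 0.233%, 720 people per cluster and 104 clusters per arm, for 90% power to detect a 75% reduction with a two-sided 5% test. Stratification plays no part in it.

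Only the protocol was available. The point does not rest on detail that a statistical analysis plan would supply, because the protocol expressly excludes the design factors from the primary model.

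**The concern.** Stratified allocation balances the arms on district and size. Variation in prevalence between strata therefore drops out of the true sampling variance of the treatment contrast. A model without strata does not know this and leaves that variation in the random-intercept variance. Its standard error then exceeds the true one.

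The offset does not repair this. It makes the expected count proportional to population, whereas a size stratum would matter because prevalence itself may differ between large and small sub-communes.

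At stake is precision. The primary objective is to estimate an effect, and an interval wider than the design warrants gives away information already paid for. Between-cluster variation is large here. The ICC of 0.0091 at prevalence 0.233% implies a coefficient of variation of √(0.0091 × 0.99767 / 0.00233) = 1.97. How much of it lies between strata is unknown.

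**Working it through.** **Inputs** (section 12, Primary outcome): p1 = 0.00233; p2 = 0.25 × p1 = 0.0005825; ICC 0.0091; m = 720; 104 clusters per arm; two-sided 5%.

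**Step 1: reproduce the protocol's figure.**
- Individually randomised n per arm = (1.960 + 1.282)² × [p1(1−p1) + p2(1−p2)] / (p1−p2)² ≈ 10,002 (10,005 with pooled variance).
- Design effect (DE) = 1 + 719 × 0.0091 = 7.543.
- Clusters per arm = 10,002 × 7.543 / 720 = 104.8, against 104 stated. Power at 104 clusters is 89.8%.

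The figure reproduces with the full ICC, so no credit was taken for stratification.

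**Step 2: let strata explain a share f of the between-cluster variance.** The documents do not give f, so it is an assumption and is varied.
- DE(f) = 1 + 719 × 0.0091 × (1 − f)
- True SE(f) = √{[p1(1−p1) + p2(1−p2)] × DE(f) / (104 × 720)}
- SE inflation without strata: r = √(7.543 / DE(f))
- Type I error without strata = 2[1 − Φ(1.96 r)]
- Power without strata = Φ(Δ/SE(f) − 1.96 r); with strata = Φ(Δ/SE(f) − 1.96), where Δ = p1 − p2

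For f = 30%: DE = 5.580; r = √(7.543/5.580) = 1.163; SE = 0.000465; Δ/SE = 3.755. Power without strata is Φ(3.755 − 2.279) = 93.0%, and with strata Φ(3.755 − 1.960) = 96.4%.

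| f | DE(f) | SE inflation | Type I error, no strata | Power, no strata | Power, with strata |
|---|---|---|---|---|---|
| 0% | 7.543 | 1.00 | 5.0% | 89.8% | 89.8% |
| 5% | 7.216 | 1.02 | 4.5% | 90.3% | 91.0% |
| 10% | 6.889 | 1.05 | 4.0% | 90.8% | 92.2% |
| 20% | 6.234 | 1.10 | 3.1% | 91.9% | 94.4% |
| 30% | 5.580 | 1.16 | 2.3% | 93.0% | 96.4% |

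**Step 3: simulation of a Poisson model with a lognormal cluster intercept** (104 + 104 clusters of 720, coefficient of variation 1.97 in both arms, nine districts; 600 to 1,000 runs per setting).
- Districts explain 30%: the unadjusted mean SE was 0.229, against a true SD of 0.201 in one set of runs and 0.221 in another. Type I error was 2.8% and 3.8%.
- Districts explain nothing: unadjusted type I error was 5.2% and 5.6%, so the SE was not too wide.
- Design ratio 0.25: power was 99.9% to 100% without district and 100% with it. One reason this exceeds Step 1 is that the formula holds the ICC equal in both arms. That implies a coefficient of variation of √(0.0091 × 0.99942 / 0.0005825) = 3.95 in the intervention arm, twice the value simulated.
- Ratio 0.5: with 30% explained, power rose from 83.5% to 89.3% in one set and from 81.5% to 86.7% in another. With 10% explained the gain was 1.9 to 3.5 points.

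**Step 4: does the form of adjustment matter?** Expected cases per control cluster are 720 × 0.00233 = 1.7, which is sparse. Type I error was 5.4% to 6.0% with nine district terms, but 6.5% to 7.7% with 18 or more fixed stratum terms. A rough quasi-Poisson check, which is not the protocol's model, with log-variance 1.6 and f = 30% gave 13.5% with 18 terms. In that same setting the unadjusted SE was about right (0.263 against 0.263).

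**The case against.** The strongest reply is that a prespecified model without covariates is a legitimate choice, and that its only fault here is caution. It does not inflate false positives. The sample size absorbs the full ICC, so the unadjusted analysis stays at or above the reproduced 89.8% power at every share tried. In the mixed-model simulations, power at the design effect is close to 100% either way. No section reports how prevalence varies by district or cluster size. A careless remedy could also do harm, since a fixed effect for every district-by-size cell is mildly anti-conservative with so few cases per cluster.

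All of that stands, and it rules out two stronger readings. A reader might infer that the standard errors are wrong whatever the data, or that the trial falls short of its 90% power. The first fails because at f = 0 nothing is lost, and the documents do not give f. The second fails because power is forgone only against an adjusted analysis, not against the plan. The larger gains seen at a ratio of 0.5 are not for the design effect. Part of them reflects slight liberality of the adjusted test: at 0% explained, where there is nothing to gain, adjustment still added 0.9 to 1.2 points.

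What the reply does not remove is the mismatch. The allocation uses two design factors and the primary model expressly excludes them, with no reason given.

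**Conclusion.** The point holds as a conditional loss of efficiency. It is not a threat to validity. If strata explain 0% to 30% of between-cluster variance, leaving them out inflates the standard error by 0% to 16%, lowers type I error from 5.0% to as little as 2.3%, and forgoes 0 to 3.4 points of power at the 75% reduction. At a modest 10% the cost is 1.4 points (92.2% − 90.8%).

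These figures rest on three assumptions: the range for f, reading 0.0091 as the overall ICC with no strata removed, and a normal approximation. The simulations agree on direction, but the gap between estimated and true SE varied from run to run and was absent in the rough check at high overdispersion. The size should be read as approximate.

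**What to change.** Replace the sentence in section 12 that excludes covariates with:

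*The primary model will account for the randomisation strata in a low-dimensional form suited to sparse counts: district as a random effect or as main effects, plus one additive population-size term, and not a fixed effect for every district-by-size cell. No other covariate enters the model.*

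Report the model without strata as supportive. Make the change before any outcome data are seen.

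The cost is one sentence and a few degrees of freedom: with district main effects, 8 district contrasts plus 1 size term, or 9, out of 208 clusters, and fewer with district as a random effect. The risk is slight liberality if too many fixed stratum terms are used, which the low-dimensional wording is meant to prevent. If the exclusion is kept, the protocol should say why and name the stratum-adjusted model as a sensitivity analysis.
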